Appendix B
Eastern Cooperative Oncology Group Performance Status Scale

ECOG Performance Status	
0	Fully active, able to carry on all predisease performance without restriction.
1	Restricted in physically strenuous activity but ambulatory and able to carry out work of a light or sedentary nature (eg, light house work or office work).
2	Ambulatory and capable of all self-care but unable to carry out any work activities. Up and about more than 50% of waking hours.
3	Capable of only limited self-care; confined to bed or chair more than 50% of waking hours.
4	Completely disabled. Cannot carry on any self-care. Totally confined to bed or chair.
5	Dead.

APPENDIX C: Study CO-1686-019 Extension Phase

OBJECTIVE OF THE EXTENSION PHASE

The purpose of the Extension Phase is to allow patients to continue on study but to avoid unnecessary collection of data that will no longer be analyzed or required for regulatory purposes, whilst maintaining an appropriate level of safety monitoring.

In addition, Amendment 5 also introduces the availability of NAT2 testing for patients, an indirect indicator of the likelihood of developing hyperglycemia and QTc prolongation. The availability and disclosure of this information to the patients's treating physician will not affect the monitoring and associated treatment guidelines for these adverse events.

INTRODUCTION

Additional information on efficacy/safety aspects

The most current clinical and non-clinical updates, in particular those pertaining to efficacy and safety data, are provided in the current Investigator's Brochure, in which integrated summaries of efficacy and safety data are presented.

Additional information relating to Hyperglycemia and QTc prolongation

The polymorphic enzyme NAT2 mediates the N-acetylation of M502 to form M544 and also plays a role in the elimination of M460. NAT2 genotype polymorphism was assessed for the group of patients who received rociletinib at 500 mg BID, 625 mg BID, 750 mg BID, and 1000 mg BID and who gave additional informed consent for genomic testing. The NAT2 genotype polymorphism testing was performed using an assay based on polymerase chain reaction (PCR) followed by mass spectrometry to identify single nucleotide polymorphisms in NAT2. Based on NAT2 genotype results, patients were classified as having "low", "intermediate", and "rapid" acetylator phenotype. Acetylator status is currently available for 635 patients. Additional testing will be completed as additional samples are received.

Adverse event and laboratory data based on NAT2 phenotype are summarized in [Appendix C, Table 1](#), [Appendix C, Table 2](#), and [Appendix C, Table 3](#). Analyses are presented by acetylator status for all doses combined, since the combined-dose findings were consistent with the findings within each dose group.

[Appendix C, Table 1](#) demonstrates that Grade 3 events are less common in patients who are classified as "rapid" acetylators. As expected, the relationship is most clear for hyperglycemia and QT-prolongation, while other adverse events of special interest (AESIs) appear to be less closely associated with acetylator status. [Appendix C, Table 2](#) shows that hyperglycemia appears to be less frequent and less severe in rapid acetylators. [Appendix C, Table 3](#) shows that QTcF prolongation on ECG appears to be less frequent and less severe in rapid acetylators.

Appendix C, Table 1. Grade 3 or Greater Treatment-emergent Adverse Events by Acetylator Status

	Overall (N = 635)		
	Slow (n=300)	Intermediate (n=259)	Rapid (n=76)
Overall	243 (81%)	194 (75%)	48 (63%)
Hyperglycemia (CT)	131 (44%)	66 (26%)	13 (17%)
QTc prolongation (CT)	44 (15%)	19 (7%)	1 (1%)
Malignant neoplasm progression	39 (13%)	39 (15%)	8 (11%)
Cataracts (CT)	12 (4%)	9 (4%)	7 (9%)
Pneumonitis (CT)	3 (1%)	4 (2%)	0
Diarrhea	13 (4%)	16 (6%)	1 (1%)

Abbreviation: CT=combined terms.

Appendix C, Table 2. Hyperglycemia Lab-shift by Acetylator Status

	Overall (N = 635)		
	Slow (n = 300)	Intermediate (n = 259)	Rapid (n = 76)
Subjects with any post-baseline glucose values > 250 mg/dL	121 (40%)	65 (25%)	17 (22%)
Subjects with 2 or more post-baseline glucose values > 250 mg/dL	51 (17%)	36 (14%)	7 (9%)
Subjects with any post-baseline glucose values > 500 mg/dL	11 (4%)	7 (3%)	1 (1%)
Subjects with 2 or more post-baseline glucose values > 500 mg/dL	3 (1%)	0 (0.0)	0 (0.0)

Appendix C, Table 3. QTcF Changes on ECG by Acetylator Status

	Overall (N = 635)		
	Slow (n = 300)	Intermediate (n = 259)	Rapid (n = 76)
QTcF Post-baseline \geq 450 msec	198 (66%)	131 (51%)	34 (45%)
QTcF Post-baseline \geq 481 msec	92 (31%)	44 (17%)	7 (9%)
QTcF Post-baseline \geq 501 msec	59 (31%)	22 (9%)	1 (1%)
Two of more within 3 days \geq 501 msec	19 (6%)	10 (4%)	0 (0.0)
QTcF Change from Baseline > 30 msec	246 (82%)	171 (66%)	47 (62%)
QTcF Change from Baseline > 60 msec	141 (47%)	57 (22%)	9 (12%)

Abbreviation: ECG=electrocardiogram.

For those patients ongoing on rociletinib trials, informed consent and testing for NAT2 polymorphism status will be offered and the results will be shared with the treating physician. It will be up to the patient in consultation with the treating physician to decide continued participation in the trial in light of the acetylator status results or whether alternative treatment options should be sought.

Regardless of acetylator status, monitoring should be the same for all patients receiving rociletinib whilst on treatment.

STUDY DESIGN

Treatment Regimen and Duration of Therapy

All patients will sign an informed consent which explains the rationale for closing the CO-1686 clinical development program for NSCLC and the option for ongoing patients to continue

receiving study treatment, should they decide to do so and/or if in the opinion of their treating physician they continue to receive clinical benefit.

Patients may continue to receive CO-1686 if the PI and patient deem it is appropriate for the patient though the availability and suitability of alternative treatment options should be considered by the treating physician and discussed with the patient. CO-1686 will be administered daily on a 28-day cycle. Dosing will be delayed or decreased according to protocol-specified toxicity criteria ([Section 7.4](#)). Each dose should continue to be taken with 8 oz. (240 mL) of water and with a meal or within 30 minutes after a meal two times per day. Tablets should be swallowed whole.

Treatment may continue until disease progression or intolerable toxicity. Please note, patients may opt to continue to receive treatment with CO-1686 following radiographic progression as outlined in the NCCN guidelines for treatment of NSCLC with EGFR TKIs if patient provides additional consent, the investigator feels it is in the patient's best interest and with sponsor approval. It is important that before deciding to continue treatment with rociletinib post progression, additional treatment options are explored and discussed with the patient by the treating physician. In general, eligible patients may include those with asymptomatic systemic progression or locally symptomatic progression, such as brain metastases amenable to local treatment, with concomitant asymptomatic systemic progression or continued systemic disease control. This must be discussed with the sponsor and will be reviewed on a case-by-case basis.

If a patient continues treatment post-progression, all Extension Phase study assessments should continue per protocol and data should be captured in the eCRF. The patient should be discontinued from treatment once it is clear that no further clinical benefit can be achieved.

Both the hyperglycemia and QTc management guidelines ([Section 7.4](#)) should be followed during this extension phase and any modifications/deviations from these guidances should be discussed and agreed upon with the sponsor prior to implementation.

Once study treatment has been discontinued and the End of Treatment visit has been completed, study participation will cease. Investigational centers will interpret tumor scans locally for the purpose of making treatment decisions and for final tumor response evaluation. The study will close once all patients have either completed participation, have transferred to a locally approved treatment access program (e.g. a named patient program) in accordance with relevant local regulations or the sponsor decides to close the study.

PATIENT ELIGIBILITY AND WITHDRAWAL CRITERIA

Eligibility and Number of Patients

This amendment applies to patients who remain on CO-1686 treatment in the CO-1686-019 study. No additional patients will be enrolled.

Withdrawal Criteria

The patient has the right to stop treatment or to withdraw from the study at any time.

Patients will continue to receive treatment until one of the following cessation criteria applies:

- Consent withdrawal at the patient's own request or at the request of their legally authorized representative.
- Progression of patient's underlying disease.
 - Post-progression treatment is permitted, at the discretion of the Investigatory and with the approval of the sponsor.
- Intercurrent illness that prevents administration of treatment (Reference [Section 7.7](#))
- Any event, adverse or otherwise, that, in the opinion of the investigator, would pose an unacceptable safety risk to the patient.
- Major noncompliance that may affect patient safety.
- Pregnancy.
- Investigator decision.

In addition, the sponsor may discontinue the trial early for any of the reasons noted in [Section 13.6](#) of the protocol.

The date and reason for cessation of treatment will be documented. Patients with ongoing SAEs will be followed until either resolution or stabilization has been determined.

STUDY PROCEDURES

Schedule of Assessments

The procedures and assessments to be performed are outlined in the Schedule of Assessments presented in [Appendix C, Table 4](#). Procedures are synchronized with administration day of treatment unless indicated. The revised evaluations should commence immediately after the patient is consented, maintaining previous treatment cycle and day sequence.

Appendix C, Table 4. Schedule of Assessments – Extension Phase

	Prior to beginning Amendment 5 Evaluations	Day 1 of each cycle	End of Treatment (28±7 days after last dose)
Informed consent	X		
Physical Examination including vision check		X	X
Vital Signs ^a and Weight		X	X
Concomitant Medications and Procedures		X	X
Contraceptive Counseling ^b			X
Serum Pregnancy Test ^c			X
Fasting Serum Chemistry ^d		X	X
Hematology ^e		X	X
Adverse Events ^f		X	X
Patient Diary ^g		X	X
CO-1686 Dispensing / Administration		X	
ECG Assessments using central ECG machine ^h		X	X
Tumor Scans ⁱ	To be performed per institutional standard of care or every 8 ± 1 weeks (every 2 cycles); scans are not required at the End of Treatment Visit		
Blood for CYP Evaluation (Optional Sampling) ^j		X	

^a = Vital signs (blood pressure, pulse, and temperature) taken predose on drug administration days.

^b = Patients are to continue using effective contraception for 12 weeks after last dose of CO-1686 and report any pregnancies during this period.

^c = Serum β-hCG to be evaluated by local lab and performed only on women of childbearing potential.

^d = Glucose must be measured following an 8 hour fast (no food or liquid other than water). Hemoglobin A1c will be measured on Day 1 of every other cycle while the patient is on study.

^e = Hematology evaluation should include reticulocytes.

^f = Patients will be monitored for AEs from the time the first dose of CO-1686 is administered through 28 days after the last dose.

^g = Patient diaries should be collected and reviewed for compliance at each visit. No diary will be dispensed at end of treatment.

^h = 12-lead ECG (in triplicate, 10-sec tracings > 2 min apart) prior to dosing up to and including Cycle 12, at a minimum. For patients who are ongoing at this time and for whom QTc has been < 470 ms throughout the study, ECG monitoring may be subsequently taken every 3rd cycle thereafter. ECGs will be performed and interpreted locally for patient care decisions; however, tracings should be submitted to the central laboratory for independent evaluation.

ⁱ = Tumor scans will no longer be required to be submitted to a central reviewer; Disease progression to continue to be assessed locally by the Investigator. If a patient discontinues treatment before progression or is continuing treatment post progression (approval from Sponsor is required), then the decision to conduct additional scans and the frequency of those scans to monitor disease progression will be the responsibility of the treating physician.

^j = Only 1 sample is needed and may be collected at any visit to enable NAT2 analysis.

Day 1 of Each Cycle

Patients will be instructed to **refrain** from taking their dose of oral CO-1686 at home on the day of their clinic visit (Day 1 of the cycle) because the dose will be taken during the clinic visit. The following procedures will be completed:

- Physical examination
 - Including a vision check as part of a standard physical exam
- Weight

- Vital signs (blood pressure, pulse, and temperature)
- 12-lead ECG (in triplicate, 10-sec tracings > 2 min apart) using central ECG machine prior to dosing, up to and including Cycle 12, at a minimum. For patients who are ongoing at this time and for whom QT has been < 470 ms throughout the study, ECG monitoring may be subsequently taken every 3rd cycle thereafter. ECGs will be performed and interpreted locally for patient care decisions; however, tracings should be submitted to the central lab for independent evaluation.
- Fasting serum chemistry (including fasting glucose). HbA1c will be measured every other cycle (Day 1 of Cycle 3, 5, 7 etc).
- Hematology (including reticulocyte count)
- Concomitant medication and procedures
- AE monitoring
- Collection and review of patient diary and CO-1686 drug return
CO-1686 tablets will be dispensed to the patient; patient diary will be provided to the patient
 - Oral CO-1686 will be administered with a meal, or within 30 minutes after a meal. The patient must also drink at least 8 ounces (240 mL) of water when taking CO-1686. Tablets should be swallowed whole.
- Tumor assessments will be performed per institution standard of care or every 8 ± 1 weeks after dosing until disease (tumor or clinical) progression. Disease progression to continue to be assessed locally by the Investigator. If a patient discontinues treatment before progression or is continuing treatment post progression (with approval from Sponsor), then the decision to conduct additional scans and the frequency of those scans to monitor disease progression will be the responsibility of the treating physician.
- (Optional) Blood for CYP Evaluation
 - Patient may consent for optional CYP sample collection if not previously collected already, and have the sample collected for NAT2 analysis
 - Sample should only be collected at a single visit

End of Treatment Visit

The following procedures will be performed for all patients 28 days (± 7 days) after the last dose of oral CO-1686:

- Physical examination
 - Including a vision check as part of a standard physical exam
- Weight
- Vital signs (blood pressure, pulse, and temperature)
- Concomitant medications and procedures since last visit
- 12-lead ECG (in triplicate, 10-sec tracings > 2 min apart)

- Fasting serum chemistry (includes fasting glucose) .
- Hematology (including reticulocyte count)
- Serum pregnancy test for women of childbearing potential
- AE monitoring (until 28 days after last dose of oral CO-1686; then only ongoing serious adverse events (SAEs) are followed until resolution or stabilization)
- Collection and review of patient diary
- Contraceptive counseling

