11.2.5.4 Vital Sign Measurements

The baseline vital sign measurement will be defined as the last value prior to or on the day of the first dose of CO-1686. The on-treatment period will be defined as the day after the first dose of CO-1686 to 28 days after the last dose of CO-1686. Vital sign measurements collected during the on-treatment period will be included in the summary tables. The vital sign measurements collected after the on-treatment period will only be presented in the data listings.

The summary of vital sign data will include descriptive statistics (N, mean, standard deviation, minimum, median, and maximum) of the maximum, minimum, and last value during the on-treatment period. Summaries using descriptive statistics of the change from baseline to the maximum, minimum, and last value during the on-treatment period will also be given.

11.2.5.5 12-lead Electrocardiograms

ECG intervals will be stratified into categories indicative of potential clinical significance. Each patient's maximum QT and QT_C intervals from the pretreatment visit and treatment period visits will be classified as ≤ 450 msec, > 450 msec to ≤ 480 msec, > 480 msec to ≤ 500 msec, and > 500 msec. For each patient's maximum change from the pretreatment ECG visit for QT and QT_C, intervals will be classified into < 30 msec, ≥ 30 msec to < 60 msec, and ≥ 60 msec. The number and percentage of patients in each classified category will be presented. Additional endpoints will include abnormal T waves and U waves and other ECG intervals and diagnostic parameters.

Descriptive statistics will be used to summarize other ECG parameters of PR, QRS, QT, and RR interval, and the corresponding changes from pretreatment ECG visit at each time point. Plots of the mean QT/QT_C over time will be provided.

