# 11.4 12-Lead Electrocardiograms

The electocardiograms (ECGs) will be centrally read for this study. The ECG measurements (an average of the triplicate measurements) will be used for the statistical analysis and all data presentations. QT intervals will be corrected for heart rate (QTc) using standard correction factors of both Fridericia's (QTcF) and Bazett's (QTcB).

Electrocardiogram (ECG) intervals will be stratified into categories indicative of potential clinical significance. Each patient's maximum QT and QTc intervals from the pretreatment visit and treatment period visits will be classified as ≤450 msec, >450 to ≤480 msec, >480 to ≤500 msec, and >500 msec. For each patient's maximum change from the pretreatment ECG visit for QT and QTc, intervals will be classified into <30 msec, ≥30 to <60 msec, and ≥60 msec. Patients will also be classified according to the CTCAE grade 3 criteria of at least 2 on treatment QTc values >500ms. The number and percentage of patients in each classified category will be presented.

Descriptive statistics may be used to summarize other ECG parameters of PR, QRS, QT, and RR interval, and the corresponding changes from pretreatment ECG visit at each time point.

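### Mean QT/QTc plots that run past Cycle 12 can be biased upward, because the extension phase allows fewer ECGs only for patients whose QTc has stayed below 470 ms

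*Protocol*

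**What the plan says.** Appendix C, Table 4 puts an ECG on Day 1 of each cycle. Footnote h asks for triplicate tracings "prior to dosing up to and including Cycle 12, at a minimum". It then allows a lighter schedule for ongoing patients "for whom QTc has been < 470 ms throughout the study, ECG monitoring may be subsequently taken every 3rd cycle thereafter". No reduction is offered to a patient who has ever reached 470 ms. The text on Day 1 procedures in the same appendix repeats the rule but sets the limit on a different interval: "for whom QT has been < 470 ms throughout the study".

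The extension ECGs remain available for analysis, since footnote h says "tracings should be submitted to the central laboratory for independent evaluation".

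Protocol 11.2.5.5 says that plots of mean QT/QTc "over time will be provided". It also plans descriptive statistics for PR, QRS, QT and RR, with "corresponding changes from pretreatment ECG visit at each time point". Neither display has a last cycle, and 11.2.1 allows no imputation. The section's other QT/QTc analysis classifies each patient's maximum value and maximum change.

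**The concern.** After Cycle 12 the chance of being measured can depend on the variable being averaged. If patients with consistently lower QTc have fewer ECGs, a raw mean at a later visit gives too much weight to patients with a past QTc of 470 ms or more. The mean then moves up even if no patient's QTc changes.

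The plot bears on a specific safety statement. Protocol 3.4.1.1 says that the QTc increase is typically evident by Day 15 and stays stable with continued dosing. A late rise produced by the schedule could be read as cumulative QTc toxicity and as evidence against that statement.

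**Working it through.** The documents give no mean QTc and no figure for this point, so there is nothing to reproduce. The check sets out the mechanism and then shows how large the effect could be under stated assumptions.

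**Inputs from Appendix C, Table 3 (635 patients)**
- Any post-baseline QTcF of 450 ms or more: (198 + 131 + 34)/635 = 363/635 = 57.2%.
- Any post-baseline QTcF of 481 ms or more: (92 + 44 + 7)/635 = 143/635 = 22.5%.
- The printed percentages in these two rows agree with their counts. In the row for 501 ms or more, 59 of 300 is 19.7%, not the printed 31%; that row is not used here.

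**Share who would qualify for the reduced schedule (assumption: each patient's maximum QTcF is normally distributed)**
- SD = (481 − 450)/(0.755 + 0.181) ≈ 33.1 ms. Mean = 450 + 0.181 × 33.1 ≈ 456 ms.
- P(maximum ≥ 470) = 1 − Φ((470 − 456)/33.1) ≈ 0.336.
- So about p = 0.664 would never have reached 470 ms.

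**Gap between the two groups**

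A simulation of 200,000 patients with 13 ECG visits through Cycle 12 was fitted to the two shares above. With an assumed within-patient SD of 5 ms, mean QTc is 429 ms in patients never at 470 ms and 483 ms in the others, a gap of d = 54 ms. With SDs of 10 and 15 ms the gaps are 474 − 421 = 53 ms and 465 − 414 = 51 ms.

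**Bias in the mean at a thinned cycle**

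Let u be the share of qualifying patients who take up the reduced schedule, and assume they all share the same third cycles. The measured mean minus the mean of all patients on treatment is

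bias = d × (1 − p) × pu/(1 − pu).

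| Uptake u | Calculation (d = 54 ms) | Bias | Simulated range, SD 5–15 ms |
|---|---|---|---|
| 0 | – | 0 ms | 0 |
| 25% | 54 × 0.336 × 0.166/0.834 | 3.6 ms | 3.4 to 3.6 |
| 50% | 54 × 0.336 × 0.332/0.668 | 9.0 ms | 8.4 to 9.0 |
| 75% | 54 × 0.336 × 0.498/0.502 | 18.0 ms | 16.8 to 18.0 |
| 100% | 54 × 0.664 | 35.9 ms | 33.6 to 35.8 |

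**If QTc later falls in the group that reached 470 ms (full uptake)**
- Fall of 20 ms: d = 34, bias 34 × 0.664 = 22.6 ms (simulated 20.3 to 22.5).
- Fall of 40 ms: d = 14, bias 14 × 0.664 = 9.3 ms (simulated 7.0 to 9.3).

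**If patients start the every-third-cycle count at different cycles (full uptake)**

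At any cycle one third of the qualifying patients are measured, so u acts as 2/3: 54 × 0.336 × 0.443/0.557 = 14.4 ms (simulated 13.5 to 14.4). This bias is present at every later cycle.

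**Which cycles are affected**

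Amendment 5 refers to a letter of June 2016. From 31 December 2014, the enrollment limit for the SAP dataset, to 1 June 2016 is 518 days, or 518/28 = 18.5 cycles. Patients in that dataset who were still on treatment were therefore at about Cycle 18 or 19, or later, when the rule could first apply. Their earlier cycles after Cycle 12 were on the Section 9 schedule of an ECG every cycle.

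**The case against.** The strongest reply is that little of this reaches a reported analysis, and that the effect is easily overstated. Several stronger readings are tempting, and the documents do not support them.

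- **A reader might infer that only patients with high QTc are measured at the cycles in between.** The reduction is optional, so patients below 470 ms can stay on every cycle. A patient who once reached 470 ms need not be high now: protocol 7.4 provides for holding and restarting at a reduced dose after Grade 3 prolongation.
- **A reader might expect a saw-tooth.** That needs all patients to share the same third cycles, and the text fixes no such calendar. With staggered starts the bias is spread over all later cycles.
- **A reader might take the bias as known.** Putting the 22.5% and 57.2% shares with a 20 to 40 ms gap gives 0.428 × 20 = 9 ms to 0.775 × 40 = 31 ms. That gap has no source in the documents, full uptake is assumed, and Table 3 pools doses and trials. It does not describe patients still on treatment after Cycle 12.
- **A reader might extend the point to the SAP.** Its data stop at 29 April 2015, before the rule existed. SAP 11.4 names no mean-QTc plot and makes by-visit summaries optional: "Descriptive statistics may be used to summarize other ECG parameters of PR, QRS, QT, and RR interval". Its wording on "the corresponding changes from pretreatment ECG visit at each time point" belongs to that optional list.
- **A reader might extend it to by-visit QTc tables.** The lists in both documents name QT, not QTc.

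It is also true that these displays are descriptive, that no test or decision rule uses them, and that the extension phase aims to avoid collecting data that will not be analyzed. All of this limits the reach and the size. It does not remove the point. Protocol 11.2.5.5 still promises the mean QT/QTc plot, extension ECGs still go to the central laboratory, and nothing in the protocol keeps them out of the plot.

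**Conclusion.** The point holds for protocol 11.2.5.5. If ECGs taken under the reduced schedule enter the mean QT/QTc plot or the by-visit QT summaries as raw means, those means can be biased upward after Cycle 12 and can resemble a late rise.

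The size cannot be determined from the documents. It is 0 ms without uptake of the reduced schedule, about 3.5 ms at 25% uptake, and up to about 35 ms at full uptake with no later fall in QTc. These figures rest on a normal distribution fitted to pooled multi-trial data, assumed within-patient SDs of 5 to 15 ms, and assumed uptake. They illustrate the mean QTc level; the effect on QT change from pretreatment was not calculated. The categories of maximum QTc do not have this averaging bias. The SAP analysis is not affected.

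Separately, Appendix C states the 470 ms criterion on QTc in Table 4 and on QT in the Day 1 procedures. The rule that selects patients for fewer ECGs is therefore itself inconsistent.

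**What to change.** In protocol 11.2.5.5 only:

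1. End the mean QT/QTc plots and the by-visit QT summaries at Cycle 12. Alternatively, include only ECGs taken under the Section 9 every-cycle schedule, before the patient moved to the Amendment 5 schedule. The second option keeps fully scheduled cycles after Cycle 12. Either option removes the schedule-driven bias.
2. Show the number of patients measured at each visit.
3. Keep the maximum-value and maximum-change categories on all data, with a note that ECG frequency after Cycle 12 could depend on earlier QTc.

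Restricting later displays to every third cycle is not a safe substitute, because no common set of cycles is fixed. SAP 11.4 needs no edit. The ECG monitoring schedule itself is not touched.

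The cost is one sentence and a visit filter; a few late-cycle points leave the plot.

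The sponsor should also reconcile the two statements of the 470 ms criterion in Appendix C (QTc in Table 4, QT in the Day 1 procedures).
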